**TRADEMARK INFORMATION**

[figure not shown]
Trademarks of the GSK group of companies	Trademarks not owned by the GSK group of companies
None	Macrobid

## 10.11. Appendix 11: Protocol Amendment History

The Protocol Amendment Summary of Changes Table for the current amendment is located directly before the Table of Contents (TOC).

### Amendment 4 05 May 2023

Section # and Name	Description of Change	Brief Rationale
1.3 Schedule of Activities: Cohort 2	Footnote added to describe home visits for outpatient visits	Allowance of home visits (with prior agreement from GSK) to ease scheduling restrictions at sites
1.3 Schedule of Activities Cohort 1 and Cohort 2	Footnote added stating baseline data will be collected at pre dose on Day 1 (except for triplicate ECG which uses Day -1 screening)  Extension of screening lab results to up to 24hr (plus 6 hrs)  Footnote added to reference Point of Care (POC) devices at screening	Clarification of baseline timepoint, extension of lab result turnaround time and allowance of POC devices at screening following prior agreement with GSK to ease site and patient burden at the screening visit
1.3 Schedule of Activities	Urine and Plasma PK predose Cohort 1 added to main SOA	To align Main SOA with detailed PK sampling SOA
1.3.1. Cohort 1: Intensive PK Profiling During an Inpatient Intervention Period	Under Urine pregnancy test Added: (for women of childbearing potential)	Added text is to clarify that the use of pregnancy testing is for women of childbearing potential.  Pregnancy testing is not required in women that are confirmed to be of nonchildbearing potential.
1.3.2. Cohort 2 Reduced PK Sampling During an Outpatient Intervention Period	Under Urine pregnancy test Added: (for women of childbearing potential)	Added text is to clarify that the use of pregnancy testing is for women of childbearing potential.  Pregnancy testing is not required in women that are confirmed to

Section # and Name	Description of Change	Brief Rationale
		be of nonchildbearing potential.
2.3.1 Risk Assessment Reproductive toxicity	Update of wording regards animal reproductive studies	Animal reproductive studies now complete.
3.Objectives and Endpoints and/or Estimands	Primary estimand on subjects who completed the planned course of treatment	Interest lies in the treatment effect of participants who completed treatment to establish proof of mechanism
3.Objectives and Endpoints	Secondary and exploratory objectives for PK updated	
Due to recruitment challenges in Cohort 1, there is a risk that the following PK parameter analysis will not be able to be conducted. The following PK parameters, which can only be measured calculated from data generated in Cohort 1, have therefore been moved to exploratory.
 
CCI
  
Urine
 
 
Amount excreted in urine (Ae) of unchanged GSK3882347, fraction of the dose excreted in urine (fe), and renal clearance (CLr)
 

5.1 Inclusion criteria	
Inclusion criteria 3 updated to increase Leukocyte esterase threshold to 2+
 
Wording now 'The
	To help increase the potential for participants to have an infection that meets the current defined evaluability criteria.

Section # and Name	Description of Change	Brief Rationale
	participant has nitrite OR pyuria ( $\geq 10$ WBC/mm  , OR $> 5$ WBC/HPF OR the presence of 2+ leukocyte esterase) from a pre-treatment clean-catch midstream urine sample based on local laboratory procedures.'	
5.2 Exclusion criteria	Exclusion criteria 11 updated to reference eGFR	Exclusion criteria 11 has referenced the units associated with estimated Glomerular Filtration Rate (eGFR= ml/min/1.73m  ) but has incorrectly associated these units with creatinine clearance (which has a standard value in ml/min). Therefore, the term creatinine clearance has been updated to eGFR. For consistency between sites, the equation for the calculation of the eGFR.
5.2 Exclusion criteria	Exclusion criteria 11 updated to remove requirement for assessment of urine albumin:creatinine ratio at screening.	Assessment of urine albumin:creatinine ratio has been removed as a requirement at screening. Participants with a history of proteinuria are excluded, as per exclusion criteria 28.  Assessment of urine protein:creatinine ratio will continue to be performed by the central labs at Day 1 predose and all further laboratory assessment timepoints specified in the SoA table.
5.2 Exclusion criteria	Exclusion criteria 26 updated to allow medical use of marijuana	Marijuana use is legal in some US states and therefore is not classed as a substance of abuse.

Section # and Name	Description of Change	Brief Rationale
	‘Substance abuse: Active substance abuse or a history of substance abuse (in the opinion of the Principal Investigator) within 6 months prior to the initial Screening visit. Note that documented medical use of marijuana or occasional recreational use of marijuana is permitted	
5.2 Exclusion criteria	Exclusion criteria 28 updated to reference proteinuria	Exclusion criteria 28 has been updated to clarify that a history of significant renal conditions includes a history of significant or chronic proteinuria.
5.2 Exclusion criteria	Exclusion criteria 30 Correction of criteria from ‘must’, to ‘does not’  The participant does not agree to adhere to the concomitant therapy restrictions as described in Section 6.8.2 from the Screening Visit through to the Follow Up Visit.	Word change of criteria to correct direction of exclusion
5.4 Screen Failures	Addition of following wording  Scheduling of Day 1 visit falls outside of 24hrs however participant will remain within 96 hours of symptom onset.	To aid scheduling of day 1 visits at site for patients as long as they remain to meet all entry criteria
6.8.2 Prohibited Meds	Text updated to the	Correction of grammar

Section # and Name	Description of Change	Brief Rationale
	
following
 
Known nephrotoxic medications (e.g. ACE inhibitors, Angiotensin receptor blockers) and regular NSAID use should be avoided
	
8.2.2 Vital Signs	Flexibility to allow semi- supine or seated positions for vital sign assessment	To allow sites to adhere to their local standard procedures
8.9 Administrative and general baseline procedures	New section added outlining justification of collection of demographic information and use of third parties	Mandated text included due to new GSK process to justify demographic collection and transparency of third-party use.
9.2 Analysis Sets	Rename ITT population to Exposed and group by actual treatment rather than randomised	Interest lies in treatment effect of actual treatment received. This population is used for listings
9.2 Analysis Sets	Update definition of micro-ITT to require “all planned doses” rather than “at least 1 dose” and rename as Micro-MPP.	Interest lies in treatment effect following 5 days dosing
CCI		
Appendix 2	Clinical Chemistry updated to reference	Exclusion criteria 11 has the values of estimated Glomerular Filtration Rate (eGFR= ml/min/

Section # and Name	Description of Change	Brief Rationale
	eGFR	1.73m  ) but has incorrectly stated creatinine clearance (which has a standard value in ml/min). Therefore, the term creatinine clearance has been adjusted to eGFR, and the clinical chemistry list updated to reflect this adjustment.
Appendix 10.2. Clinical Local Laboratory Tests	Guidance on POC assessment at screening	Allowance of POC devices at screening following prior agreement with GSK to ease site and patient burden at the screening visit
Appendix 11 Acronym table	eGFR and POC added	New acronyms
Appendix 12: Protocol Amendment History-PA3 Summary Table	Updated the word “and” to “or” in the text Updated definition of pyuria from >15WBC/HPF and presence of 3+ /large leukocyte esterase to ≥10WBC/mm  or >5WBC/ HPF or presence of leukocyte esterase.	For Clarification
11 References	Reference for CKD-EPI added	Reference for equations to calculate eGFR

**Amendment 3** 07 Oct 2022

**Overall Rationale for the Amendment:** The following updates were made to reduce patient burden within this study, expand enrollment criteria and administrative changes.

Section # and Name	Description of Change	Brief Rationale
1.3 Schedule of Activities (SoA) Cohort 1 and Cohort 2  8. Study Assessments and Procedures	Pre-screen ICF available for local urinalysis (dipstick) and pregnancy test. Added pre-screening language for clarification in the SoA tables and Section 8	A pre-screen ICF was added to obtain consent for the collection of a urine sample to support study enrollment (specifically inclusion #3)
2.3.1 Risk Assessment	Reproductive toxicity added as a potential risk and CYP3A4 induction risk.	
This addition is not based on any new emerging safety information. Instead, it is to clearly state the unknown risk of drug exposure in pregnant women in this section and align risk language with wording already entered in the protocol (Section 10.4) and study documents.
 
Pre-existing protocol inclusion criteria for WOCBP including contraceptive guidance and pregnancy testing remain in place. Changes added to expand the required duration of contraception use for WOCBP using hormonal contraceptives (due to potential CYP3A4 induction risk) and to clearly state in this section that double barrier contraception required as already stated in Section 10.4).

5.1 Inclusion Criteria #2	Updated the onset of clinical signs and symptoms from $\leq 72$ hours to $< 96$ hours	To allow participants further flexibility to enroll within the study.
5.1 Inclusion Criteria #3  8.1.2 Microbiology Outcome and Response	Updated definition of pyuria from $> 15 \text{ WBC/HPF}$ or presence of $3+ / \text{large leukocyte esterase}$ to $\geq 10 \text{ WBC/mm}^3$ or $> 5 \text{ WBC/HPF}$ or	To expand definition of pyuria and therefore further participant inclusion into the study.

Section # and Name	Description of Change	Brief Rationale
	presence of leukocyte esterase.	
5.1 Inclusion Criteria #5	Expanded and added clarification to contraceptive requirements for WOCBP using hormonal contraceptives	
This amendment is not based on any new emerging safety information. Instead, it is to align with the updated risk benefit section and align with wording already entered in the protocol (Section 10.4) and study documents.
 
Pre-existing protocol inclusion criteria for WOCBP including contraceptive guidance and pregnancy testing remain in place. Changes added to expand the required duration of contraception use for WOCBP using hormonal contraceptives (due to potential CYP3A4 induction risk) and to clearly state in this section that double barrier contraception required as already stated in Section 10.4).

5.2. Exclusion Criteria #29	Prior/Concomitant Therapy: updated antimicrobials or systemic antifungals used within 4 weeks to within 1 week of study entry.	
Changes needed to align with the Concomitant Therapy Section (6.8.2) of the protocol.
 
Dalbavancin or oritavancin exclusion changed to ten weeks before study start due to the long half-life compared to other antimicrobials.

6.8.2 Prohibited Medication and Non-Drug Therapies	Updated antimicrobials or systemic antifungals used within 4 weeks to within 1 week of study entry with the exception of dalbavancin and oritavancin.	
It was determined that a one week period prior to study entry is sufficient.
 
Dalbavancin or oritavancin exclusion changed to ten weeks before entry due to longer half-life values compared to other antimicrobials.

Section # and Name	Description of Change	Brief Rationale
	Removed restrictions on substrates of BCRP and OATP1B1 (e.g. statins)	PBPK modelling has superseded static equations which initially flagged a potential for GSK3882347 to perpetrate DDIs with substrates of BCRP and OATP1B1. The PBPK model has since confirmed there is a low risk of clinically meaningful DDIs with substrates of these transporters.
8 Study Assessments and Procedures  1.3 Schedule of Activities (SoA) Cohort 1 and Cohort 2	Addition of potential e-consent	To allow participants further flexibility to enroll within the study.
Various Sections	Minor editorial updates	For clarification

**Amendment 2** 24Feb2022

Section # and Name	Description of Change	Brief Rationale
2.3.1. Risk Assessment	Summary of nonclinical findings and mitigation strategy added to the Risk Assessment table.	Pre-clinical risk associated with renal changes in rats identified as a potential risk of clinical significance.
5.2. Exclusion Criteria #11	Creatinine clearance value changed from <60 mL/min/1.73m  to <90 mL/min/1.73m  .	Pre-clinical risk associated with renal changes in rats identified.
5.2. Exclusion Criteria #28	Criteria updated to include a specific list of conditions that could be exclusionary.	List added to emphasize the desire for relatively healthy study population.
5.2. Exclusion Criteria #30	Reference to the relevant protocol section added, Baseline Visit updated to Screening Visit and ToC changes to Follow up visit.	Changes needed for clarity and to align with the Concomitant Therapy Section (6.8.2) of the protocol.

Section # and Name	Description of Change	Brief Rationale
5.2. Exclusion Criteria #37	Deleted.	Changes to Exclusion #30 made #37 redundant.
6.3. Measures to Minimize Bias: Randomization and Blinding	Sentence added regarding the use of an unblinded team for the purpose of the Interim Analysis.	Addition to emphasize the use of an internal unblinded team to review and conduct interim analysis.
6.8 Concomitant Therapy	Section restructured and potential drug-drug interactions added.	Restructured for clarity, additional potential drug-drug interaction to reflect FDA feedback and specific details around nephrotoxic drugs added.
New Section: 8.2.4.2 Management of participants with changes in serum creatinine	Section 8.2.4.2 added.	Section added to ensure appropriate monitoring of serum creatinine changes.
CCI		
10.2. Appendix 2: Clinical Laboratory Tests Table 3 Protocol-required Safety Laboratory Tests	Additional expected results added to table and text for the collection of a SoC microbiology urine sample at screening added.	Lab appendix updated to better reflect laboratory testing originally included during set-up of assessments (e.g., addition of absolute value included and reported in central lab standard panels and calculations for serum and urine creatinine) and to clarify a microbiology urine sample at screening can be obtained as part of SoC.
10.7.2. Procedures During COVID-19 Pandemic	Language added to describe circumstances and procedures for alternate COVID-19 testing.	Due to potential inconsistencies in availability of rapid antigen tests kits (e.g., rise in variants creating high demand/low supply of kits) alternate testing measures were added for these types of circumstances.
Various locations	Clerical updates.	Minor corrections to clean document.

**Amendment 1** 17-Dec-2021

**Overall Rationale for the Amendment:** An inclusion and exclusion criterion were modified to enhance study recruitment and the microbiological response definitions were clarified based on FDA advice.

Section # and Name	Description of Change	Brief Rationale
1.3.2. Cohort Reduced PK Sampling During an Outpatient Intervention Period SoA Table	UTI Clinical Signs and Symptom Score Assessment at Post Dose on Day 1 was removed.	The assessment at this timepoint was added in error.
5.1. Inclusion Criteria	Inclusion 3 edited to permit participant inclusion with nitrite or pyuria positive urinalysis.	Edit to inclusion criteria to expand the potential participant involvement and number of evaluable participants in the study considering the sensitivities of the assays. Wording 'Nitrite AND Pyuria' replaced with Nitrite OR Pyuria'.
CCI		
9.3.2. Primary Endpoint(s)/Estimands(s) Analysis	Definition of microbiological response clarified.	Based on FDA advice, the definitions for microbiological response were revised to clarify that a reduction in any/all E. coli counts at the ToC visit determine the microbiological response.
Various locations	Typo and formatting issues corrected.	Minor corrections to clean document.

**VERSION HISTORY**

SAP Version	Approval Date	Protocol Version (Date) on which SAP is Based	Change	Rationale
Original	18-Nov-2021	20-Aug-2021	CCI	
Amendment 1	23-Aug-2023	05-May-2023		

SAP Version	Approval Date	Protocol Version (Date) on which SAP is Based	Change	Rationale
			CCI	
Amendment 2	03-Jan-2025	10-Jun-2024		
Amendment 3	20 Jan 2025	10-Jun-2024		

SAP Version	Approval Date	Protocol Version (Date) on which SAP is Based	Change	Rationale
			CCI	

## 1. INTRODUCTION

The purpose of this SAP is to describe the planned analysis to be included in the Clinical Study Report for Protocol 212943. Details of the planned CCI final analyses, are provided.

Additional details with regards to data handling conventions and the specification of data displays will be provided in the Output and Programming Specification (OPS) document.

### Objectives, Estimands and Endpoints

Objectives	Endpoints
Primary	

 
To assess the microbiological efficacy of GSK3882347 at the Test of Cure (ToC) visit in participants with uUTI who have qualifying E. coli at baseline
 
	
 
Microbiological response at the ToC Visit
 

Secondary	

 
To evaluate the safety and tolerability following CCI oral dosing for 5 days of GSK3882347 in participants with uUTI
 
	
 
Occurrence of adverse events (AEs) and serious adverse events (SAEs)
 
Clinically significant changes from baseline in laboratory values (haematology, chemistry and urinalysis), vital signs and 12-lead electrocardiogram (ECG) readings at each visit
 

 
To evaluate the plasma and urine pharmacokinetic (PK) concentrations following CCI oral dosing for 5 days of GSK3882347 in participants with uUTI
 
	
Plasma:
 
 
GSK3882347 concentration
 
 
Urine
 
 
Urine concentration at 22-24h interval collection post-dose
 

Objectives	Endpoints
Exploratory*	
CCI	

To evaluate the resolution of clinical symptoms over time of GSK3882347 in participants with uUTI caused by E. coli

	

Clinical resolution response on Day 2 through to Day 6 (when collected and as data permit), ToC and Follow-up Visit

To evaluate the resolution of clinical symptoms over time of GSK3882347 in participants with uUTI caused by E. coli using an exploratory scoring system

	

Clinical symptom score outcome and response on Days 1 through to Day 6 (when collected and as data permit), ToC and Follow-up Visit

CCI	

Objectives	Endpoints

CCI
 

	

\*Some exploratory data may not be available until after the main database lock and may be analysed/reported separately.

### 1.1.1. Estimand for Primary Endpoint

The primary clinical question of interest is: *What is the microbiological response for GSK3882347 assessed at ToC in participants with acute uUTI caused by E. coli at Baseline who completed the planned course of treatment (5 days) and had no major deviations from protocol that would prevent evaluation of microbiological response (as defined in the protocol deviation rules document). Use of rescue medication after last dose of study intervention will be set to non-responder in the endpoint definition.*

The Primary estimand is described by the following attributes:

- Population: Female participants with acute uUTI with a qualifying baseline *E. coli* (Section 6.4) at baseline who completed the planned course of treatment (5 days) and had no major deviations from protocol that would prevent evaluation of microbiological response
- Treatment condition: GSK3882347 CCI mg given orally CCI for 5 days or Nitrofurantoin 100mg given orally twice daily for 5 days.
- Variable: Microbiological response at ToC visit (see Section 4.2.1)
- Summary measure: Frequency and percentage of participants with microbiological response (responder/non-responder) in GSK3882347 treatment group
- Main intercurrent events anticipated:

- Use of rescue medication prior to ToC visit- Composite strategy
- This intercurrent event is captured through the definitions of microbiological response (see Section 4.2.1). Hence the participants who take rescue medication prior to ToC visit will be considered as non-responders.
- Participants who are lost to follow-up prior to ToC, have a missing/ unevaluable sample at ToC, discontinue study treatment due to any reason (withdrawal of consent/AEs/missed doses) will not be included in the analysis and may be replaced at the discretion of the Sponsor.
- Rationale for estimand:

Use of rescue medication may impact microbiological outcomes and its use implies that the treatment the participant received is not working, therefore, the definition of a successful microbiological response precludes the use of rescue medications. In this small, early phase, proof of mechanism study, interest lies in the treatment effect of participants who completed the planned course of treatment and follow important components of the study protocol to establish proof of mechanism.

### 1.1.2. Estimand for Secondary Endpoints

The secondary clinical questions of interests are,

1. *What is the incidence of AEs, SAEs and clinically significant changes in safety data from baseline (laboratory, vitals and ECG) following CCI oral dosing for 5 days of GSK3882347 (or less than 5 days if study intervention is discontinued for any reason) in adult female participants with uUTI?*

The estimand is described by the following attributes:

- Population: Female participants with acute uUTI.
- Treatment condition: GSK3882347 CCI mg given orally CCI for 5 days or Nitrofurantoin 100mg given orally twice daily for 5 days.
- Variables:
  - Occurrence of adverse events (AEs) and serious adverse events (SAEs)
  - Clinically significant changes from baseline in laboratory values (haematology, chemistry and urinalysis), vital signs and 12 lead electrocardiogram (ECG) readings at each visit.
- Summary measure: Frequency and percentages for AEs, SAEs, laboratory values, vital signs and ECG values.
- Main intercurrent events anticipated:
  - Use of rescue medication - Treatment policy strategy
  - Discontinuation from the treatment due to any reason (withdrawal of consent /AEs (if not part of the endpoint definition, for example, in AE and SAE)/missed doses)-Treatment policy strategy

The interest lies in the full safety profile regardless of the occurrence of these intercurrent events. Hence safety data evaluated throughout the study will be considered for the analysis.

2. *To evaluate the plasma and urine PK concentrations following CCI oral dosing for 5 days of GSK3882347 or until discontinuation of treatment*

The estimand is described by the following attributes:

- Population: Female participants with acute uUTI
- Treatment condition: GSK3882347 given orally CCI for 5 days
- Variables:
  - Plasma:
    - GSK3882347 trough concentration on Day 1 and Day 5 (Ctau)
  - Urine:
    - Urine concentration at 22-24h collection following dose on Day 1 and Day 5
- Summary measure: Mean, 95% confidence interval (CI), standard deviation (SD), median, minimum, and maximum and geometric mean, 95% CI of geometric mean, and coefficient of variation (CV) of geometric mean, for log transformed data.
- Main intercurrent events anticipated:
  - Discontinuation from the treatment due to any reasons (AEs/withdrawal of consent/missed doses)
  - Administered incorrect dose based on adherence records

All these intercurrent events will be handled using while on treatment strategy as interest lies in PK data until whilst participants are receiving study intervention

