### 6.8.3. Rescue Medicine

If participants do not respond clinically (participants experience new, worsening or non-resolving signs and symptoms of uUTI) to randomised medication, they should be given rescue medication. They will be considered a treatment failure and will be provided rescue medication by site as per SoC [Gupta, 2011].

Use of rescue medications is allowable at any time during the study. The requirement for the use of rescue medications should be assessed by the Investigator in accordance with site procedure and treatment guidelines [Gupta, 2011]. If clinically acceptable (and onset of a severe infection is not suspected), rescue medication should be postponed until the next clinical symptom resolution assessment during the On-Therapy period.

Pathogen identification or in vitro resistance of recovered uropathogens alone, is not a reason for study treatment discontinuation through the On-Therapy period. Patients can resolve their infection spontaneously and in the absence of treatment [Little, 2009].

The date and time of rescue medication administration as well as the name and dosage regimen of the rescue medication must be recorded.

Rescue medication to be prescribed by Site Investigator as required and as assessed by the Investigator and in consultation with the Medical Monitor if required by the Investigator. The decision to prescribe rescue medication resides with the Investigator. A combined clinical and laboratory (e.g. serum creatinine and other haematological and biochemical parameters) assessment should be used to prior to withdrawal of study intervention.

The Investigator can request the participant's baseline, enrolling microbiology culture to help in the assessment and additional suitable SoC if required [Gupta, 2011]. Note: The potential for a drug-drug interaction with next line therapy (e.g., trimethoprim-sulfamethoxazole) has been reviewed and is permitted in the study.

If antibiotic rescue medication is given, the participant will complete an early discontinuation visit as per the SoA and will not be required to attend any other subsequent visits.

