### **7.1. Discontinuation of Study Intervention**

In rare instances, it may be necessary for a participant to permanently discontinue study intervention. All Participants who discontinue study intervention should have an early withdrawal/discontinuation visit. Plasma and urine PK sample(s) should be collected as per SoA on the corresponding day as the participants last day of PK sample collection (s).

Participants may voluntarily discontinue study intervention at any time. The investigator may also, at his or her discretion, discontinue the participant from study intervention at any time and initiate appropriate alternative therapy (Section [6.8.3](#). Rescue Medication).

Reasons for study intervention discontinuation may include the following:

- Adverse event
- Investigator discretion
- Lost to follow-up
- Participant decision
- Participant reached protocol-defined stopping criteria.

The reason for study intervention discontinuation will be recorded in the eCRF.

Participants who discontinue study intervention for the reasons above, but not due to the requirement of rescue medication, will not be considered withdrawn from the study and should attend all subsequent study visits (see Section [1.3](#)). They will remain in the study to be evaluated for safety and efficacy, PK samples will not be collected following the treatment discontinuation and early withdrawal/discontinuation visit. See the SoA for data to be collected at the time of discontinuation of study intervention and follow-up and for any further evaluations that need to be completed.

If study intervention is permanently discontinued due to the requirement of rescue medication, the participant will complete an early study discontinuation visit and no other visits will be required.

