		respectively CCI from a quantitative bacteriological culture of a pre-treatment clean-catch midstream urine specimen.	
Amendment 3	CCI		
	
 
For primary endpoint estimand: Use of rescue medication will be set to non-responder in the endpoint definition.
 
	
 
Use of rescue medication after last dose of study intervention will be set to non-responder in the endpoint definition.
 
	
 
Wording for primary estimand updated to clarify that rescue medication use for population of interest would only occur following the 5 day dosing period.
 

	
 
For secondary endpoints estimand: Use of rescue medication – While on treatment strategy
 
	
 
Use of rescue medication – Treatment policy strategy
 
	
 
Strategy for handling of ICE for estimand for Secondary endpoint – Safety so that all safety data is presented in summaries.
 

	
 
For secondary endpoints estimand: estimand specified for plasma and urine PK parameters
 
	
 
For secondary endpoints estimand: estimand specified for plasma and urine PK concentrations
 
	
 
Updated to align with protocol defined secondary endpoints
 

CCI

CCI

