### 6.3.2. Study Period

Assessments and events will be classified according to the time of occurrence relative to the study intervention period.

**Pre-Intervention** is defined as time prior to the first dose of study intervention.

**On-Intervention** is defined as time from first dose to End of Study (end of all follow up visits). If time of assessment or study intervention is not collected, the following assessment on the first dose date will be assumed to be taken prior to the first dose and therefore considered pre-intervention: ECG, Lab, and vital signs, and first dose date and time is considered the start of on-intervention for AE and concomitant medication.

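### The safety estimand applies treatment policy to rescue, but required visits stop after antibiotic rescue, so crude AE percentages can pool truncated with full follow-up

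*SAP*

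**What the plan says.** For the safety estimand, SAP 1.1.2 lists "Use of rescue medication - Treatment policy strategy" and aims at the whole safety profile whether or not rescue occurs: "Hence safety data evaluated throughout the study will be considered for the analysis". SAP Table 2 records this as a deliberate Amendment 3 change from the protocol's while-on-treatment strategy, made for "Safety so that all safety data is presented in summaries".

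The summary measure is "Frequency and percentages for AEs, SAEs, laboratory values, vital signs and ECG values". The AE tables in SAP 4.5.2 show on-intervention events, and SAP 6.3.2 sets the window: "On-Intervention is defined as time from first dose to End of Study". SAP 4.5.1 summarises exposure to study treatment. The public text has no summary of AE observation time.

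The protocol treats rescue differently from other reasons for stopping. After antibiotic rescue the participant "will complete an early discontinuation visit as per the SoA and will not be required to attend any other subsequent visits" (Protocol 6.8.3). Protocol 7.1 says that when treatment is stopped because rescue is needed, "the participant will complete an early study discontinuation visit and no other visits will be required". Under the same section, participants who stop for other reasons attend all later visits.

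Protocol 8.3.1 nevertheless has all AEs collected until the follow-up visit at the scheduled timepoints, with no exception for rescue. Protocol 10.3.4 has nonserious AEs followed until that visit.

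**The concern.** Treatment policy for rescue needs safety data from after rescue. The SAP changed the strategy, but the protocol's visit rule after rescue stayed as it was. The participants who may be observed for less time are therefore those in whom treatment failed, and a crude percentage does not show this.

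The reason for shortened observation may also differ by arm. Protocol 2.3.3 calls the efficacy of GSK3882347 unknown and nitrofurantoin a recommended treatment. Participants are dosed before culture confirms *E. coli* (Protocol 8.1.2), and the test drug is specific to *E. coli* (Protocol 4.2). More rescue on GSK3882347 is therefore plausible. Its AE column would then rest on less observation time than the column beside it. Nitrofurantoin is in the study so that safety reporting is unbiased (Protocol 9.3.1), and safety is tabulated by treatment group (SAP 4.5), so readers will compare the two.

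The gap is not confined to AEs. Laboratory, ECG and vital-sign changes are endpoints at each visit, and the ToC and Follow-up values may be missing after rescue. Renal change is a listed risk in Protocol 2.3.1.

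**Working it through.** **Observation time from the schedule.** The stated maximum duration of 31 days reproduces as 28 + 3, and Follow-up falls on Days 25 to 31. ToC falls on Day 5 + 5 = 10 to Day 5 + 8 = 13. Rescue at a symptom assessment on Days 2 to 6 leaves about 2 to 6 days of required observation, and rescue at ToC leaves 10 to 13. Protocol 6.8.3 allows rescue at any time, so later rescue leaves more.

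**Inputs that must be assumed.** The documents give no AE rate, no rescue rate by arm and no distribution of rescue timing. I take a true 28-day AE incidence I = 30% in both arms, rescue proportions r = 20% (GSK3882347) and 5% (nitrofurantoin), and AE observation ending at Day d = 6 for rescued participants.

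**Constant hazard.**
- h = −ln(1 − I)/28 = −ln(0.70)/28 = 0.01274 per day
- Incidence by Day 6 = 1 − exp(−6h) = 7.4%
- Crude incidence = r × 7.4% + (1 − r) × 30%
- GSK3882347: 0.20 × 0.0736 + 0.80 × 0.30 = 25.5%
- Nitrofurantoin: 0.05 × 0.0736 + 0.95 × 0.30 = 28.9%
- Spurious difference: −3.4 points
- Mean observation: 0.20 × 6 + 0.80 × 28 = 23.6 days versus 0.05 × 6 + 0.95 × 28 = 26.9 days

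**Early clustering.** Suppose 80% of first events occur by Day 6, so a rescued participant has incidence 0.80 × 30% = 24%.
- GSK3882347: 0.20 × 0.24 + 0.80 × 0.30 = 28.8%
- Nitrofurantoin: 0.05 × 0.24 + 0.95 × 0.30 = 29.7%
- Spurious difference: −0.9 points

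**Sensitivity to the assumptions.**

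| Scenario | Difference (GSK3882347 − nitrofurantoin) |
|---|---|
| Constant hazard, I = 30%, Day 6, rescue 20% vs 20% | 0 (25.5% in both arms, against a true 30%) |
| Constant hazard, I = 30%, Day 12, rescue 20% vs 5% | −2.4 points |
| Constant hazard, I = 30%, Day 6, rescue 40% vs 10% | −6.8 points |
| Constant hazard, I 20 to 40%, Day 4 to 12, unequal rescue from 20% vs 5% to 60% vs 10% | −1.6 to −16.5 points |
| 80% of first events by Day 6, I = 30%, same unequal rescue range | −0.9 to −3.0 points |

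**Scale.** With 122 randomized 3:1 (91.5 and 30.5, taken as 92 and 30), the 95% half-width of a difference at 30% is 1.96 × √(0.21/92 + 0.21/30) = 18.9 points.

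**The case against.** The strongest reply is that collection does not simply stop at rescue. Later visits are not required, but they are not barred. Protocol 8.3.1 runs AE collection to the follow-up visit. Protocol 8.3.3 and 10.3.4 follow SAEs until they resolve or stabilise, and 10.3.4 follows nonserious AEs to the follow-up visit. Protocol 7.2 follows participants discontinued for an AE, and 8.2.4 repeats clinically significant laboratory values. This stands. A reader might infer that no post-rescue safety data exist, and the documents do not support that. What is at risk is mainly newly arising AEs and scheduled measurements after the early discontinuation visit.

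The direction of any bias can also be questioned. Symptoms from lack of efficacy count as AEs when they meet the definition (Protocol 10.3.1), and reactions to the rescue drug that are captured also count. Both would raise incidence in the arm with more rescue, and the calculation leaves both out.

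The effect is small beside the sampling uncertainty, and no formal comparison is planned. Disposition, exposure, concomitant medication including rescue, and AE relatedness and intensity are already to be summarised. Further displays may be in the Output and Programming Specification, which is not public. This lowers the weight of the point, but none of the planned summaries described in the SAP shows how long each arm was observed for AEs.

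Finally, treatment policy can be read as using whatever was collected, with gaps treated as missing data. That is reasonable, but the SAP then needs to say that the gaps exist and that rescue causes them.

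**Conclusion.** The mismatch holds on the documents alone. The SAP seeks the full safety profile regardless of rescue, the protocol requires no visits beyond an early discontinuation visit after antibiotic rescue, and other protocol sections say AE collection continues. The AE tables give rescued participants the same weight as those observed for about 28 days.

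The size is conditional. At 30% incidence, rescue at Day 6 and 20% versus 5% rescued, the distortion is about 3.4 points with a constant hazard and about 0.9 points if first events cluster early. Five-day dosing makes clustering at least as plausible. Equal rescue rates give no difference between arms, although both incidences are then too low.

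Three stronger readings are tempting. One is that the arms are observed unequally: no rescue rates are given, so this is a risk and not a fact. Another is that rescued participants have about one week of data: that fits on-therapy rescue only. The third is that GSK3882347 will look safer than it is: this needs more rescue on that arm and no offset from failure symptoms or rescue-drug reactions recorded as AEs.

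**What to change.** In SAP 4.5.2, keep the planned tables and add, by arm:

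1. A summary of AE observation time, from first dose to last AE contact.
2. An AE table restricted to first dose through the Day 6 visit. Anyone rescued before Day 6 may still be observed for less, so read it with item 1.
3. A Kaplan-Meier cumulative incidence of first AE, censored at last AE contact. This is preferable to a rate per person-day, which assumes a constant hazard. It does assume that censored participants have the same later AE risk as those still observed, and that should be stated.

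In SAP 1.1.2, keep treatment policy and say that post-rescue safety data are incomplete under Protocol 6.8.3 and 7.1. Relabelling the strategy as observation only up to rescue would largely undo the sponsor's documented change, so I do not recommend it.

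Protocol 6.8.3 and 7.1 must be reconciled with 8.3.1 and 10.3.4 on AE collection after rescue.

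The cost is a few extra displays from existing data and some SAP wording. Any change to protocol text would go through the usual amendment approval (Protocol 10.1.1).
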